12.0 DATA COLLECTION

Data will be collected prior to randomisation (to establish eligibility to participate and assess baseline functioning), and at follow-up: 2, 5 and 12 months after randomisation.

12.1 Data to assess eligibility and covariates

At baseline eligibility will be assessed using the Autism Diagnostic Observation Schedule [1] and the Autism Diagnostic Interview-Revised [2]. In order to minimize inconvenience for parents and children the results of any recent ADOS assessment shall be used in lieu of baseline data (so long as this was completed within six weeks of their entry into the study). To take part in the study potential participants will need to meet criteria for autism spectrum disorder on the ADOS and on two of the three domains of the ADI-R. This combination of data from direct observation and interviews with parents has been used to establish eligibility in previous high quality trials of interventions for children with ASD [11, 13].

In addition to collecting basic demographic data on age, sex, ethnicity, socioeconomic status and education level the child's level of cognitive ability will be assessed using the Kaufman Assessment Battery for Children (K-ABC) [10]. In cases where the application of the K-ABC is not possible due to the child's level of cognitive functioning, researchers will assign the child to one of three categories: no, mild, or moderate/ profound mental retardation, using World Health Organisation (ICD-10) criteria [35].

12.2. Outcome measures

The primary outcome measure is the severity of autism symptoms using the social communication algorithm which is derived from the ADOS [1], which will be assessed by a trained researcher who is masked to allocation status. We have selected this measure because of its strong psychometric properties including sensitivity to change [1], and because it has been widely used in other randomised trials of children with autism [11-13]. Secondary outcomes are:

- 1) Social Responsiveness Scale [14] a carer based assessment of the severity of autism spectrum symptoms that has high inter-rater and test-retest reliability [15-16]
- 2) Questionnaire on Resources and Stress Friedrich Short Form a widely used measure of parental stress that has been validated among parents of children with autism [17].

3) Warwick and Edinburgh Well Being Schedule, a short validated measure of mental well-being [33].

All outcome measures will be assessed at baseline, 2, 5 and 12 months.

13.0 DATA ANALYSIS

As the study is pragmatic in design, the primary analysis will be by intention to treat. Descriptive analysis will be performed to examine the distribution of each outcome of each group at baseline, at the end of intervention and the end of follow-up, and differences in baseline variables between the two comparison groups. Generalised estimating equations (GEE) shall be used to compare and test changes of the primary and secondary outcomes from baseline to twelve months between the intervention and control group. GEE allows for the analysis of longitudinal data while accounting for correlation among repeated observations for each participant. GEE will also be used to examine dose effect relationships and to explore possible confounding effects of site or relevant subgroups such as age or level of cognitive impairment.

Before carrying out GEE analysis, sensitivity analyses shall be conducted to examine data missing mechanism to decide whether imputation approaches are necessary.

The analytic strategy applies to both primary and secondary outcomes. A detailed analysis plan with templates of statistical tables will be developed for the data monitoring and ethics committee. Statistical software SPSS and MLwiN will be used for the analyses.

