All music therapy sessions will last 30 minutes and be delivered by trained music therapists who have experience of working with children with ASD and are registered with the Health Care Professions Council. Therapists will deliver improvisational music therapy in accordance with consensus guidelines which have been developed from practice in previous studies [3-6]. To ensure treatment fidelity, therapists will be asked to document the content of sessions and video-record sessions. Notes from sessions will be used during monthly supervision and video-recordings will be monitored by the lead music therapist in the study.

At baseline eligibility will be established and the child's level of cognitive ability will be assessed using the Kaufman Assessment Battery for Children [10]. The primary outcome measure is the severity of autism symptoms using the social communication algorithm, which is derived from the ADOS [1]. This will be assessed by a trained researcher who is masked to allocation status. The measure has been selected because of its strong psychometric properties, including sensitivity to change [1], and because it has been widely used in other randomised trials of children with autism [11-13].

The main secondary outcomes are the Social Responsiveness Scale [14] - a carer based assessment of the severity of autism spectrum symptoms that has high inter-rater and test-retest reliability [15-16]. In addition to these outcomes which are being used across all centres in the international study, the UK-arm of the trial will include two additional items completed by parents/ guardians of children who take part in the study: the Short-Form

Parenting Stress index, a widely used and validated measure of difficulties in parent-child interactions [17], and the Warwick and Edinburgh Well Being Schedule, a short validated measure of mental well-being [33].

All outcome measures will be assessed 2, 5 and 12 months after randomisation, with the primary end-point being at 5 months.

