The main data analysis will be conducted by statisticians based in the main centre in Norway. All primary analyses will be based on intention to treat. Descriptive analysis shall be performed to examine the distribution of each outcome in each group at baseline, at the end of intervention and the end of follow-up and differences in baseline variables between the two main comparison groups (music therapy plus enhanced treatment as usual versus enhanced treatment as usual alone). Following assessment of normality, treatment effects will be analysed using a generalized estimating equations (GEE) approach that allows for analysis of longitudinal data while accounting for correlation among repeated observations for each participant [32]. GEE analyses will also be used to examine dose-effect relationships and to explore effects of covariates including site, age and sub-types of ASD.

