11.3 Sample size calculation for the main trial

A total sample of 300 needs to be recruited in the study as a whole. Previous trials of improvisational music therapy for children with ASD have reported medium effect sizes associated with active intervention. A Cochrane review of music therapy for children with ASD calculated a Standardised Mean Difference of 0.50 for gestural communication skills and 0.36 for verbal communication skills [6].

A sample of 235 patients will provide 90% power to detect a medium effect size of the intervention on the social communication scale of the ADOS score at 12 months with a 5% level of statistical significance [32]. To take account of possible clustering at the level of study therapists and study centres and a drop out we have inflated the total sample required to 300. Loss to follow-up in trials of psychosocial intervention for children with autism spectrum disorder tends to be low. The PACT trial of parent mediated communication focused treatment reported a follow-up rate of 96% at 13 months [11].

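### The planned GEE tests change from baseline without naming baseline ADOS as a covariate, and a look at the missing data decides whether to impute

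*Protocol*

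**What the plan says.** **Method and contrast.** Protocol Section 13.0 states that GEE "shall be used to compare and test changes of the primary and secondary outcomes from baseline to twelve months" between intervention and control, and applies this strategy to primary and secondary outcomes alike. Section 2.0 places the main test earlier, "with the primary end-point being at 5 months", and the primary hypothesis (Section 4.0, Study Hypotheses) agrees with 5 months.

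**Covariates.** Section 2.0 plans GEE "to explore effects of covariates including site, age and sub-types of ASD". Section 13.0 plans to "explore possible confounding effects of site or relevant subgroups such as age or level of cognitive impairment". Neither list contains the baseline value of the outcome.

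**Baseline data.** Section 12.2 says: "All outcome measures will be assessed at baseline, 2, 5 and 12 months". Section 12.1 makes the ADOS part of eligibility and adds that "the results of any recent ADOS assessment shall be used in lieu of baseline data", provided it was done within six weeks of entry.

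**Missing data.** Before the GEE, "sensitivity analyses shall be conducted to examine data missing mechanism to decide whether imputation approaches are necessary" (Section 13.0). The section gives no criterion for that decision and names no imputation method.

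**The concern.** A comparison of raw changes subtracts the whole baseline score from each follow-up score. Unless baseline and follow-up are almost perfectly correlated, this over-corrects and carries baseline noise into the treatment contrast. Entering baseline as a covariate lets the data set the weight and is never less precise in large samples. Nothing more need be collected, so any precision lost by leaving it out is lost for no return.

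The missing-data step is a separate matter. The observed data can show that dropout is related to recorded scores. They cannot show that, given those scores, it is unrelated to the unseen ones. A preliminary look therefore cannot establish that imputation is unnecessary, and it makes the form of the primary analysis depend on the trial's own data.

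**Working it through.** **Inputs.** From the protocol: 1:1 for control against pooled music therapy (2:1:1, Section 5.6); 235 children before inflation, 90% power, 5% significance (Section 11.3); standardised differences of 0.50 and 0.36 (Section 11.3); 96% follow-up in a cited trial, so about 4% loss (Section 11.3). Assumed: a two-sided test, equal variances at each visit, and ρ, for which the protocol has no value.

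**Step 1. The plan's own figure.** The protocol gives no precision figure for the change analysis. The nearest is "A sample of 235 patients will provide 90% power to detect a medium effect size of the intervention on the social communication scale". With N = 4(1.960+1.282)²/d², rounded up within each arm, d = 0.50 needs 170 and d = 0.36 needs 326. Solving for N = 235 gives d = 2(3.242)/√235 = 0.423. So 235 is not reproduced from either stated effect. That is a separate matter and nothing below depends on it; 0.423 serves only as a convenient effect size.

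**Step 2. Precision.** With complete data and separate arm means at every visit, including baseline, the GEE contrast is the difference in mean changes whatever the working correlation. In units of the outcome variance:

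- change: 1 + 1 − 2ρ = 2(1−ρ)
- baseline-adjusted: 1 − ρ²
- ratio, adjusted to change: (1+ρ)/2
- gain in information: 2/(1+ρ) − 1

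| Assumed ρ | 2(1−ρ) | 1−ρ² | Gain | N giving the precision of 235 by change | Power at 235, d = 0.423: change / adjusted |
|---|---|---|---|---|---|
| 0.3 | 1.40 | 0.91 | 54% | 153 | 78% / 93% |
| 0.5 | 1.00 | 0.75 | 33% | 176 | 90% / 96% |
| 0.6 | 0.80 | 0.64 | 25% | 188 | 95% / 98% |
| 0.7 | 0.60 | 0.51 | 18% | 200 | 99% / 99.5% |
| 0.8 | 0.40 | 0.36 | 11% | 212 | 99.9% / 100% |
| 0.9 | 0.20 | 0.19 | 5% | 223 | 100% / 100% |

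Below ρ = 0.5 the change variance exceeds 1, so the change score is then worse than ignoring baseline. A simulation with 300 children and 4,000 runs per value gave gains of 30%, 24%, 20% and 11% at ρ of 0.5 to 0.8, in line with the formula. The power columns ignore clustering.

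**Step 3. Missing data.** Two simulations, both with ρ = 0.6 and dropout depending on an observed earlier score. Effects are in SD, shown without the minus sign.

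| Setting | Dropout | GEE, independence | GEE, exchangeable | Likelihood model | Truth |
|---|---|---|---|---|---|
| A: N = 300, driven by month-2 score | 4.0% v 2.9% | 0.439 | 0.463 | 0.463 | 0.425 |
| A | 12.6% v 6.9% | 0.358 | 0.424 | 0.425 | 0.425 |
| A | 21% v 7% | 0.323–0.327 | 0.429 | 0.429–0.433 | 0.425 |
| B: N = 235, driven by month-5 score in opposite directions by arm | 4.6% | 0.348 | 0.420 | 0.419 | 0.42 |
| B | 12.3% | 0.246 | 0.421 | 0.421 | 0.42 |
| B | 23.1% | 0.112 | 0.421 | 0.421 | 0.42 |

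Near 4% loss, independence GEE differs from the likelihood model by 0.463 − 0.439 = 0.024 SD in A and by 0.419 − 0.348 = 0.071 SD in B, a deliberately severe case. In the first row of A every method lies above the truth, by up to 0.038, which points to simulation error. Only the gap between methods should be read there, and only roughly. Exchangeable GEE, which is the correct structure in these data, matches the likelihood model to within 0.004 throughout.

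**The case against.** **The wording does not exclude baseline adjustment.** A GEE with baseline as a covariate, or with the arms constrained equal at baseline, also tests change. Section 13.0 announces a detailed analysis plan, where covariates and working correlation usually sit. This stands, and it makes the precision point conditional. It does not remove it: the protocol names change as the quantity tested and lists covariates twice, each time without the baseline score.

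**A reader might infer that 11% to 33% is simply lost.** The protocol does not support that. The range is ρ from 0.8 to 0.5, and no ρ is given. Nor is there a figure for extra noise from a reused ADOS up to six weeks old.

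**A reader might also infer that GEE is biased here and must give way to a mixed model.** That needs an independence working correlation, which the protocol nowhere names, and for a large bias it needs dropout well above the 4% cited. Sections 2.0 and 13.0 both describe GEE as accounting for within-child correlation. The main analysis is run by the Norwegian centre with GEE (Section 2.0), and the UK arm follows the parent study's methods (Section 7.0). Replacing it is a debatable preference that the UK protocol could not settle alone.

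**The missingness check has a use.** It can reveal departures from missing completely at random, and imputation under missing at random would deal with those. That is correct. The objection is only to letting the check choose the primary method.

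**Conclusion.** The point holds in a limited form. The protocol fixes a test of change and omits baseline ADOS from its named covariates. If that is carried out as an unadjusted contrast, adjustment would be worth 33% to 11% more information for ρ of 0.5 to 0.8, and 54% to 5% across 0.3 to 0.9. The benefit in power is material at low ρ and negligible at high ρ. The result assumes equal variances and complete data, and is nil if baseline is already modelled.

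The imputation rule is badly fixed in principle, because the data it inspects cannot answer the question put to them. Its likely effect is small at the cited loss, about 0.02 to 0.07 SD even with an independence working correlation, and largely absent with a correct one. That reassurance rests on dropout staying near 4%. Section 11.3 inflates 235 to 300 for clustering and dropout together, so the loss actually planned for is not stated.

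**What to change.** 1. **Model.** Keep GEE. State that the 2-, 5- and 12-month scores are the responses, with arm, visit, arm by visit and the baseline value of the same outcome as covariates, and that the 5-month contrast is primary. Name the working correlation and use robust standard errors.
2. **Missing data.** Remove the step in which the data decide on imputation. Fix one primary approach valid under missing at random, for example multiple imputation before the GEE using arm, baseline and all follow-up scores, or a likelihood-based model. Use the missingness checks only to inform sensitivity analyses, including a prespecified one for data missing not at random.

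**Cost.** No extra data or participants. It takes a change of wording, agreement with the Norwegian centre so that the UK and international analyses match, and some programming for imputation if that route is chosen. If the analysis plan already contains these terms, aligning Section 13.0 with it is enough.

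### The sample size allows for therapist clustering, but the stated GEE accounts only for correlation within the child, so the standard error of the main comparison is too small if the therapist ICC is positive

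*Protocol*

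**What the plan says.** Protocol section 11.3 starts from this calculation: "A sample of 235 patients will provide 90% power to detect a medium effect size of the intervention", tested "with a 5% level of statistical significance". It then enlarges the total to 300 and gives the reason: "To take account of possible clustering at the level of study therapists and study centres and a drop out we have inflated the total sample". It states no ICC, no number of children per therapist and no planned dropout rate. It remarks that loss tends to be low in this field and cites one trial that "reported a follow-up rate of 96% at 13 months".

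Section 13.0 names GEE for both primary and secondary outcomes and describes what it handles: "GEE allows for the analysis of longitudinal data while accounting for correlation among repeated observations for each participant". Section 2.0 describes it in the same way. In section 13.0 site enters only as something for GEE to examine, to "explore possible confounding effects of site"; in section 2.0 it is one of several covariates to explore. Neither section mentions therapist. Section 13.0 lists SPSS and MLwiN as software and promises a detailed analysis plan.

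Two design features matter. Children are randomised individually, 2:1:1, so control and pooled music therapy are equal in size (section 5.6). Music therapy sessions are individual and arranged only for the two active arms (sections 5.6 and 6.1).

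**The concern.** The design recruits extra children for a correlation that the described analysis does not use. Several children share a music therapist. If therapists differ in effectiveness, those children's outcomes are correlated, and the mean of the music therapy group is less precise than a child-level calculation suggests. Control children have no music therapist, so the problem is one-sided and randomising children does not remove it.

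At stake are the confidence interval and p value of the primary comparison. The interval would be too narrow and the test would reject too often, and the children added to pay for clustering would instead make the result look more precise than it is.

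**Working it through.** **1. The plan's own figure.** For two equal groups, two-sided 5%, 90% power and SD 1, total N = 4(1.960 + 1.282)²/d². The protocol gives no number for a medium effect, only a "Standardised Mean Difference of 0.50 for gestural communication skills and 0.36 for verbal communication skills". Rounding up to equal groups:

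| d | Total N |
|---|---|
| 0.50 | 170 |
| 0.43 (midpoint of 0.36 and 0.50) | 228 |
| 0.36 | 326 |

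A total of 235 corresponds to d = 3.242 × √(4/235) = 0.423. So 235 is plausible for pooled music therapy versus control, but it cannot be confirmed.

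**2. How much clustering the inflation can hold.** With dropout fraction q, the design effect left is DE = 300(1 − q)/235. If all of it were real correlation that inflates the variance of the treatment difference and the analysis ignored it, the true type I error would be 2[1 − Φ(1.96/√DE)].

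| Dropout q (assumed) | DE | Type I error |
|---|---|---|
| 0% | 1.277 | 8.3% |
| 4% | 1.226 | 7.7% |
| 10% | 1.149 | 6.7% |
| 15% | 1.085 | 6.0% |
| 20% | 1.021 | 5.2% |
| 21.7% (= 1 − 235/300) | 1.000 | 5.0% |

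At 4% loss, 235/0.96 = 245, so about 55 of the 65 added children would be for clustering. Near 22% loss, none would be.

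**3. Music-therapist clustering alone.** With m children per therapist, the variance of the music therapy mean is multiplied by 1 + (m − 1)ICC and that of the control mean by 1. With equal groups, the variance of the difference is multiplied by f = [1 + 1 + (m − 1)ICC]/2. The child-only standard error is then 1/√f of the true one, and type I error is 2[1 − Φ(1.96/√f)].

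The values of m and ICC are assumptions. For m, 50 UK music therapy children over six areas give 50/12 = 4.17 with two therapists per area and 50/6 = 8.33 with one.

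| m | ICC | f | SE ratio | Type I error |
|---|---|---|---|---|
| 4.17 | 0.02 | 1.032 | 0.98 | 5.4% |
| 4.17 | 0.05 | 1.079 | 0.96 | 5.9% |
| 4.17 | 0.10 | 1.158 | 0.93 | 6.9% |
| 8.33 | 0.02 | 1.073 | 0.97 | 5.9% |
| 8.33 | 0.05 | 1.183 | 0.92 | 7.2% |
| 8.33 | 0.10 | 1.367 | 0.86 | 9.4% |

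A wider grid (m from 5 to 15, ICC 0.01 to 0.10) runs from 5.2% to 13.3%.

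**4. Centre and therapist separated by simulation.** The set-up was 4,000 runs, 10 centres of 30 children, arms balanced within centre and two music therapists per centre (7.5 children each), analysed at child level.

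| Centre ICC | Therapist ICC | SE ratio | Type I error |
|---|---|---|---|
| 0 | 0 | 1.00 | 5.1% |
| 0.05 | 0 | 1.03 | 4.3% |
| 0.10 | 0 | 1.03 | 4.4% |
| 0 | 0.05 | 0.92 | 7.0% |
| 0 | 0.10 | 0.86 | 9.4% |
| 0.05 | 0.05 | 0.93 | 7.4% |

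Therapist clustering shrinks the standard error about as the formula predicts. Centre clustering alone does not.

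**The case against.** **The detail may sit in the analysis plan.** Cluster unit, random effects and small-sample corrections are often left there, the protocol promises such a plan, and MLwiN fits multilevel models. The quoted sentence describes what GEE can do; it does not say that therapist correlation will be ignored. This stands to the extent that the error is a risk of following the text as written, not a certainty. It does not remove the mismatch: the protocol chooses a method, says twice which correlation it covers, and leaves out a correlation that its own sample size allows for. Naming software does not state a therapist term.

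**Centre clustering.** Since section 11.3 names centres too, a reader might infer that ignoring them also makes the standard error too small. The design does not support this. Children are the unit randomised, and with arms balanced within centre the child-only standard error is about right or slightly large. Section 5.6 does not say whether randomisation is stratified by centre, so balance is an assumption, and a treatment effect that varies by centre could change the picture.

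**The 7.7%.** A reader might take this as the sponsor's own implied error rate. It is not. The 96% is another trial's follow-up rate, and the figure also treats the whole allowance, centre share included, as variance of the treatment difference.

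**The caseload.** The UK numbers do not describe the primary analysis, which is international, planned for 300 children and run from Norway. One therapist per area also fits poorly with section 11.1, which speaks of music therapists in the plural. The caseloads are illustrations only.

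**Conclusion.** The point holds for therapists and not for centres. Section 11.3 plans for therapist correlation, and the analysis in sections 2.0 and 13.0 accounts only for correlation within the child. Followed as written, the standard error of music therapy versus control is too small whenever the therapist ICC is positive.

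The size cannot be settled from the protocol. With about 4 to 8 children per therapist and an ICC of 0.02 to 0.10, both assumed, the standard error is understated by roughly 2% to 14% and a nominal 5% test runs at about 5.4% to 9.4%. These figures use a normal reference and carry no further penalty for having few therapists. The error is moderate and may be small, but it favours finding a benefit and is easy to prevent.

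**What to change.** In section 13.0, state that the primary analysis accounts for therapist correlation in the music therapy arms, in one of two ways:

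- a mixed model with repeated measures within child and a random therapist effect in the music therapy arms only, each control child forming its own cluster, with degrees of freedom that reflect the number of therapists; or
- GEE with the therapist as the cluster for the robust variance (each control child again its own cluster) and a small-sample correction.

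Include site as a covariate in the primary model instead of only exploring it, and record a therapist identifier for each child. Section 6.4 already has therapists document every session, so the added data collection is slight.

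The cost is a wider confidence interval, and it can be substantial with few therapists. With six therapists and about 5 degrees of freedom, for example, the critical value is 2.57 instead of 1.96, an interval about 31% wider before any change in the variance. Where a site has only one music therapist, the therapist effect cannot be separated from a treatment effect that differs by site. Both are reasons to settle the method, and to count the therapists across the international trial, before outcomes are unblinded.
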